# Maintenance of a Clean, Moist Ulcer Environment

One of the key elements to optimal wound healing is maintaining a moisture balance. Too much moisture and the wound become macerated; too little moisture and the essential healing processes cannot function. During Screening and SOC Run-In Periods: A commercially available hydrogel will be applied topically to the cDFU twice daily instead of the Test Product. Hydrogel will be applied during V1 and V2 and Test Product gel during V3 onward. The gel will be applied topically to the target cDFU twice daily (roughly every 12 hours at the same times of day) for four weeks (treatment period). Optimum evening treatment would occur at bedtime, once the subject is in bed for the evening. After application of each dose of the Test Product is complete, the wound will be dressed as per the following: Mepitel or equivalent will be trimmed to cover the entire dimension of the ulcer and overlaid into the ulcer, followed by Tegaderm dressing covering the entire dimension of the ulcer. Padding and Coban Lite 2- layer dressing will be placed over the Mepitel, or equivalent, covered with Tegaderm. Application of Test Product or any gel should not occur on the day of the final visit or on the day of an early term visit.

The dressing should be kept dry during showering.

# **Debridement of the Target Ulcer**

Ulcer debridement is an essential technique and standard of care in the treatment of diabetic foot ulcerations. It is important to remove all non-viable and necrotic material from the target ulcer during V1 and V2 if needed. Sharp excisional debridement is allowed at V1 and V2, only light sharp scalpel debridement is allowed at V3, V4, V5 and V6. Light sharp scalpel debridement consists of the following:

- The index ulcer and surround skin are prepped with water or Saline
- Anesthesia, topical or injected is applied to the ulcer as necessary to reduce subject discomfort
- Remove any non-viable and necrotic tissue or slough using a scalpel or scissors
- If there is a noticeable "edge effect" on the periphery of the index ulcer, debride back to the adherent epidermis

• Excessive bleeding is controlled by using direct pressure only

No debridement is allowed at V7. During V8 either sharp excisional debridement or light sharp scalpel debridement is allowed, based on Investigator discretion. Particular care should be taken to protect healthy tissue, which has a red or deep pink (granulation tissue) appearance, this tissue should not be disrupted during debridement.

If any anesthetic medications are used for debridement, they should be added to the Concomitant Medication page of the eCRF. If extensive surgical debridement is necessary during the run-in period (i.e., general anesthesia is required), the subject is not a candidate for this trial. Likewise, if other forms of debridement (e.g., enzymatic) are required during run-in based on the opinion of the treating clinician, the subject should be screen failed.

The use of silver nitrate sticks, styptic pencils or electro-cautery is prohibited as these coagulation methods induce further tissue damage.

## Wound Debridement Procedures V1 and V2:

Assess pain level and determine appropriate method of pain control.

- Cleanse wound with sterile saline.
- Utilize sterile tissue scissors, forceps, surgical blade and/or other appropriate surgical instruments to remove devitalized tissue, as clinically indicated.
- Following debridement, cleanse wound with sterile saline.
- Achieve hemostasis
- Apply appropriate wound dressing.

The test article will not be applied to the ulcer bed until complete hemostasis has been attained. Further debridement may be performed as required throughout the treatment period, as determined by the investigator or appropriately trained and qualified designee. Debridement may be performed by either the investigator or appropriately trained and qualified designee but should be performed by the same individual throughout the duration of the clinical study.

V1: Sharp excisional debridement is required (unless contraindicated in the opinion of the investigator).

V2: Sharp excisional debridement is permitted.

#### **Wound Debridement Procedures V3 through V8:**

V3, V4, V5, V6: Only light sharp scalpel debridement is allowed.

V7 and ET: No debridement allowed.

V8: Sharp excisional debridement or Light sharp scalpel debridement allowed.

During the Treatment Phase of the trial, other forms of debridement are NOT permitted. If this should happen, the type of debridement should be noted in the CRF; using other forms of debridement besides light debridement more than once during the treatment phase will result in the subject being withdrawn from the trial.

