#### 5.5. **Follow-up Safety Period**

A 14-day follow-up safety and cDFU evaluation visit will be scheduled for all study subjects and will include assessments as per the Schedule of Events and as detailed above for V8.

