- Run-in Ulcer Assessment: Visual examination of chronic ulcer before and after debridement
- Sharp excisional debridement is allowed if necessary at Investigator's discretion
- Pre and post debridement digital photos taken by site personnel, if debridement is required. Two
  photos are to be taken from a focal distance of 18 inches, and one photo taken close-up for a total
  of three digital images
- Employ an advanced digital imaging system to accurately measure the target foot ulcer dimensions following debridement
- Evaluate wound healing and discontinue any subject with a  $\ge 30\%$  or greater reduction in area as shown by the advanced digital imaging measurements
- Continued offloading applied in accordance with Appendix 6
- Hydrogel and SOC dressing applied in accordance with the Appendix 4

Visit 3 (Day 0) Baseline: All subjects will return after the screening period for assessment of study participation criteria and if these are satisfied, the subjects will be randomly assigned to Nu-3 gel or placebo gel treatment. Subject disease assessments will be performed as specified in the schedule of events table.

- Vital signs measurements: Weight, temperature, resting blood pressure, heart rate, and respiratory rate. Vital signs are to be obtained prior to collecting laboratory samples
- Urine pregnancy test for WOCBP prior to randomization.
- Serum pregnancy test will also be conducted for WOCBP

- 12 Lead ECG
- Safety Laboratory tests
- Baseline Ulcer Assessment: Visual examination of chronic ulcer before and after debridement (if required, only LIGHT debridement is allowed)
- Two wound swabs, one for culture and one for microflora examination are taken BEFORE debridement
- Light debridement, only if required
- Digital photos should be taken pre and post debridement, if debridement is required. Two photos
  are to be taken from a focal distance of 18 inches, and one photo taken close-up for a total of three
  digital images
- Employ an advanced digital imaging system to accurately measure the target foot ulcer dimensions following debridement
- Subject randomized within electronic RTSM, obtaining kit number
- Subjects will be provided with his/her first designated test product kit and instructed to apply the product twice daily for 1 weeks (7±2 days). Test product application will be demonstrated, and subject instruction sheet reviewed, using the assigned test product

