- Continue offloading applied in accordance with Appendix 6

If the ulcer remains open at visit 7, subjects will be given a supply of non-abrasive bandages and written instructions on weekly ulcer care until the Day 42 follow up visit (Visit 8). In addition, subjects will be told to call if there is any worsening of the ulcer with regard to pain, signs of infection, or swelling.

Standardized offloading will continue until the final study visit (Day 42±2 days) regardless of wound healing status.

Visit 8 (Day 42±2) End of Study (EOS) Visit: The subject shall attend final end-of-study 42±2 days post

Randomization. At this follow-up visit, the subject will undergo the following procedures and evaluations.

- Vital signs measurements including weight, temperature, resting blood pressure, heart rate, and respiratory rate. Vital signs are to be obtained prior to collecting laboratory samples
- 12 Lead ECG
- Physical examination
- Safety Laboratory Tests
- For females of child-bearing potential: pregnancy test (serum) to be performed
- Ulcer Assessment: Visual examination of chronic ulcer.
- Take digital photos with the digital camera provided by sponsor. Two photos are to be taken from a focal distance of 18 inches, and one photo taken close-up for a total of three digital images
- Employ an advanced digital imaging system to accurately measure the target foot ulcer dimensions
- Record all adverse events (local and systemic), concurrent procedures, and changes in concomitant medications during the study on the source documents and case report forms (eCRFs)
- Physician may perform or not perform debridement according to his practice standards
- Offloading ends

Early Termination Visit: If a subject withdraws prior to completing the study, the reason for withdrawal will be documented. If a subject withdraws early due to a Serious Adverse Event, he/she will be followed until resolution/stabilization of the SAE.

If a subject prematurely withdraws from the study, subject will be asked to complete the study procedures and evaluations performed in the final study visit at the time of withdrawal from the study:

- Vital signs measurements including weight, temperature, resting blood pressure, heart rate, and respiratory rate. Vital signs are to be obtained prior to collecting laboratory samples
- 12 Lead ECG
- Physical examination
- Safety Laboratory Tests
- For females of child-bearing potential: serum pregnancy test to be performed.

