## 10. DISCONTINUATION/WITHDRAWAL CRITERIA

# 10.1. Discontinuation of Study Treatment

Participation in this study and receiving the study treatment is voluntary. A subject can withdraw from the study treatment at any time. The Principal Investigator/treating physician based on his/her clinical judgement and evaluation may at his/her discretion discontinue study treatment for safety, behavioral, compliance, or administrative reasons.

If the subject withdraws consent for study treatment after beginning, study visits and all study procedures should still be completed. The sponsor may retain and continue to use any data collected during the study for a subject who has a withdrawal of consent for study treatment.

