## 11. ADVERSE EVENTS

The definitions of an AE or SAE is provided in Appendix 2.

AEs will be reported by the subject (or, when appropriate, by a caregiver, surrogate, or the subject's legally authorized representative).

The investigator and any designees are responsible for detecting, documenting, and recording events that meet the definition of an AE or SAE and remain responsible for following up AEs that are serious, considered related to the study treatment or study procedures, or that caused the subject to discontinue the study (see Appendix 2).

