# 11.1. Time Period and Frequency for Collecting AE and SAE Information

All AEs and SAEs will be collected from the signing of the ICF until the safety follow-up visit at Day 42 at the time points specified in the Schedule of Events.

All SAEs will be recorded and reported to the sponsor or designee within 24 hours, as indicated in Appendix 2. The investigator will submit any updated SAE data to the sponsor within 24 hours of it being available.

Investigators are not obligated to actively seek AE or SAE in former study subjects. However, if the investigator learns of any SAE, including a death, at any time after a subject has been discharged from the study, and he/she considers the event to be reasonably related to the study treatment or study participation, the investigator must promptly notify the sponsor.

The method of recording, evaluating, and assessing causality of AE and SAE and the procedures for completing and transmitting SAE reports are provided in Appendix 2.

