#### Statistical methodology

#### Missing data

\*For calculation purposes, days to healing = date ulcer is first healed – date of randomization.

SAP: LLA-Nu3-CLIN002 Page 6 of 21

Missing data may be the result of missed visits, subjects lost to follow-up or who have died, and may be endpoint data or covariate data. Missing continuous outcome data will be imputed in this study using the LOCF (last observation carried forward). If wound healing outcomes are missing these will be imputed as follows: (a) If an event removes the index ulcer, such as an amputation, the outcome will be scored as not healed; (b) If a subject dies, the outcome will be scored as not healed; (c) If a subject is withdrawn from the study, the outcome will be scored as not healed; and (d) for all remaining non-healed index ulcers in the drug groups, the outcomes will be based on non-right-censored outcomes in the SOC group to weight outcomes.

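### As written, repeated non-light debridement takes a subject out of the trial rather than only off study gel, so scheduled safety follow-up stops short of Day 42

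*Protocol*

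**What the plan says.** During treatment only light debridement is permitted at V3 to V6, and none at V7. Protocol Appendix 4 tolerates one breach, to be noted in the CRF; after that, "using other forms of debridement besides light debridement more than once during the treatment phase will result in the subject being withdrawn from the trial".

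The protocol has two separate statuses. Section 10.1 covers stopping treatment: "If the subject withdraws consent for study treatment after beginning, study visits and all study procedures should still be completed". Section 10.2 covers leaving the study and contains no such requirement; it refers to the Schedule of Events for what is collected at discontinuation and afterwards. For a withdrawn subject that schedule has a single ET column. Section 8 (Early Termination Visit) says the "subject will be asked to complete the study procedures and evaluations performed in the final study visit at the time of withdrawal". The SAP's Brief Trial Description likewise ends the visit series when a subject is withdrawn.

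On adverse events, Section 11.1 plans collection to Day 42 but adds: "Investigators are not obligated to actively seek AE or SAE in former study subjects". Under Section 11, investigators "remain responsible for following up AEs that are serious, considered related to the study treatment or study procedures", or that led to discontinuation. Section 5.5 states: "A 14-day follow-up safety and cDFU evaluation visit will be scheduled for all study subjects".

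In the SAP, Missing data gives this rule for missing healing outcomes: "If a subject is withdrawn from the study, the outcome will be scored as not healed". Missing continuous outcomes are carried forward. The Patient Populations table keeps withdrawn subjects in the ITT and safety sets and leaves them out of MITT and per-protocol.

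**The concern.** A prohibited debridement is a co-intervention that muddies the reading of wound healing. That is a reason to stop study gel and to keep the subject out of the per-protocol analysis. It is not a reason to stop watching for harm, yet the rule chooses the status under which scheduled observation ends.

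Safety and tolerability is the primary objective, each dose has 12 active subjects, and each cohort's safety data go to the DMC. Single events can matter: Sections 5.1 and 7.3 set the MTD as the level below one at which a DLT is seen, and a DLT in the first cohort halts the study. After withdrawal, a new event could go uncounted unless the investigator happens to learn of a related SAE.

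Subjects who need repeated stronger debridement plausibly have a poorer wound course, so the loss may be related to outcome. That is inference; nothing in the documents establishes it. Study offloading also ends at the early termination visit, whereas other subjects keep it to Day 42. Healing and ulcer area that could have been observed are replaced by the SAP's imputation rules.

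**Working it through.** The plan has no figure to reproduce here, since no sample size was calculated. Its allocation is consistent: 16 × 3/4 = 12 active and 16 × 1/4 = 4 placebo per cohort, so 24 + 8 = 32 over two cohorts.

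**Step 1: does follow-up survive withdrawal?** Three texts might restore it.
- Section 10.1 keeps visits going, but only for withdrawal of consent for study treatment.
- Section 5.5 schedules the safety visit for every study subject, but does not say whether that includes someone already withdrawn. The SAP's Brief Trial Description points the other way.
- Section 10.2 mentions further evaluations but sends the reader to a schedule with only an ET column.

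None clearly keeps this subject in follow-up to Day 42.

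**Step 2: size per affected subject.**

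Inputs from the Schedule of Events: V4 = Day 7, V5 = Day 14, V6 = Day 21, V7 = Day 28, V8 = Day 42. The endpoint window is 28 days (Section 4), and the post-baseline part of AE collection is 42 days (Section 11.1).

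Assumption: both uses happen at scheduled visits, the first no earlier than V4, so the second falls at V5, V6 or V7.

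Days lost = 28 − day of withdrawal, or 42 − day of withdrawal. Arm denominators: 12 × 28 = 336 and 12 × 42 = 504 subject-days. Pooled placebo to Day 42: 8 × 42 = 336.

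| Second use | Lost of 28 days | Lost of 42 days | Visits lost | Dose arm, 28-day window | Dose arm, to Day 42 | Pooled placebo, to Day 42 |
|---|---|---|---|---|---|---|
| Day 14 | 14 (50%) | 28 (66.7%) | 3 | 14/336 = 4.2% | 28/504 = 5.6% | 28/336 = 8.3% |
| Day 21 | 7 (25%) | 21 (50%) | 2 | 7/336 = 2.1% | 21/504 = 4.2% | 21/336 = 6.25% |
| Day 28 | 0 (0%) | 14 (33.3%) | 1 | 0% | 14/504 = 2.8% | 14/336 = 4.2% |

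For withdrawal at Day 14, the two later scheduled ECG and laboratory sets (V7 and V8) are replaced by one early termination set taken at withdrawal.

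**Step 3: conditional case.** A second use at Day 7 is possible only if V3 debridement counts as treatment phase. At V3, debridement is listed before the step "Subject randomized within electronic RTSM, obtaining kit number", so this is doubtful. If it does count, the loss is 35/42 = 83.3% of days to Day 42, 21/28 = 75% of the 28-day window, and 4 visits. That is 35/504 = 6.9% of a dose arm or 35/336 = 10.4% of pooled placebo.

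**Step 4: what one subject is worth.** With event rate p, the chance of seeing at least one event in n subjects is 1 − (1 − p)^n. The rates are assumptions, not in the documents. Going from 12 to 11 subjects:
- p = 5%: 0.460 to 0.431
- p = 10%: 0.718 to 0.686
- p = 20%: 0.931 to 0.914

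These drops are upper bounds, because a withdrawn subject still contributes partial follow-up.

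**The case against.** The trigger needs two breaches of an explicit prohibition, so it may never be met. Two breaches may simply reflect site non-compliance, for which Section 10.2 allows withdrawal. Safety is not abandoned: the early termination visit includes vital signs, examination, ECG, laboratory tests, imaging and, before Day 28, swabs. SAEs are followed to resolution or stabilisation (Section 11.3). Gangrene, osteomyelitis and grade 3–4 events trigger a treatment pause on their own (Section 12.3.4). On the 28-day endpoint the cost is at most 4.2% of one arm's subject-days per affected subject in the base case. All of this stands, and it limits the size of the point without closing the gap.

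The frequency argument is weaker than it looks. Under its V1 and V2 heading, Appendix 4 also allows further debridement as needed throughout treatment without naming a type, so a site could breach the rule in good faith.

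The strongest objection is practical: merely changing trial withdrawal to gel discontinuation would not work. The Synopsis (Administration) bars any other gel during treatment, so a retained subject would have no permitted moist-wound gel, and the light-only rule would still bind a clinician who judges stronger debridement necessary. This is right, and the fix must deal with both.

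A reader might infer that the rule contradicts Section 10.1, or that these subjects vanish from safety follow-up and analysis. The documents support neither. Section 10.1 covers a different event, known serious or related events are still followed, and the SAP keeps withdrawn subjects in the safety set.

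**Conclusion.** The point holds as a design weakness that is cheap to repair. As written, the rule exchanges the remaining scheduled visits for one early termination visit and ends active AE seeking before Day 42.

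Per affected subject the loss is 14 to 28 of 42 post-baseline days (33% to 67%), and 0% to 50% of the 28-day window. This assumes the second breach falls at V5, V6 or V7; the Day 7 case depends on a doubtful reading of V3. The number of such subjects is unknown and may be zero. The days counted are days without active AE seeking, not days without any safety oversight. It would go too far to say that the rule biases the safety results: that would require knowing who breaches it and why, and the documents are silent on both.

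**What to change.** In Protocol Appendix 4, replace withdrawal from the trial with wording such as:

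> discontinued from study gel and recorded as a major protocol violation (excluded from the per-protocol set); the subject is asked to complete all remaining visits and safety assessments through Day 42, using the commercial hydrogel and standard of care, with any further debridement at the investigator's discretion and recorded in the CRF.

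Add a matching exception to the Synopsis (Administration) ban on other gels during treatment. This extends the principle of Section 10.1 to a case that section does not itself cover.

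The visits are already scheduled and the SAP population definitions need no change. There are three costs:
- ITT healing data will include outcomes observed after a prohibited co-intervention, where the subject would otherwise be scored not healed.
- The subject will also enter MITT, which excludes withdrawn subjects but keeps major violators.
- TEAE summaries will include off-gel events, so each should be flagged by onset relative to last dose.

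The per-protocol set, which already leaves out major violators, gives the healing analysis without these subjects.

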# **APPENDIX 5: MICROBIOLOGICAL ASSESSMENTS**

Two wound swabs of ulcer will be sent for aerobic and anaerobic cultures of contaminating microbes, which will be performed by a central microbiology lab, and for molecular evaluation of microflora at V1, V3, V4, V5, V6 and V7 (and/or at early termination). Suitable culture samples must be obtained via wound swab. Biopsy, curettage, and needle aspirations are not allowed. If suitable culture material is not available due to healing of the ulcer, this will be documented by the investigator. All wound swabs will be obtained BEFORE debridement.

The eradication/persistence of each baseline pathogenic species will be determined based on culture results reported by the laboratory. If a subject's culture result is missing for V7, the baseline pathogen will be presumed eradicated if a) ulcer closure is achieved, b) because of ulcer healing there is a lack of suitable tissue sample/culturable material (as documented by the investigator), or c) the culture result is otherwise missing, and pathogen eradication was achieved in the last available culture result. In all other circumstances, baseline pathogen persistence (i.e., not eradication) will be presumed.

# Process and Procedure for Microbiological and Microflora Swabs

The process for obtaining, storing and shipping swabs can be found in the study reference manual.

